9.5 Exploratory PD Analysis

9.5.1 Continuous Glucose Monitoring

Continuous glucose monitoring data will be collected during the exercise, test meal assessments, and overnight periods (Day -1 from **CCL and and Destination** on Day 1) as both duration (in minutes and percentage of time in range with glucose values between 70 and 180 mg/dL (3.9 and 10.0 mmol/L), inclusive. The parameters to be derived from the CGM data are:

- duration (in minutes) and percentage of time of hypoglycemia with glucose values <54 and <70 mg/dL (3.0 and 3.9 mmol/L)
- duration (in minutes) and percentage of time of hyperglycemia with glucose values >180 and >250 mg/dL (10.0 and 13.9 mmol/L)
- mean glucose
- overall variability (CV and SD)

The parameters will be summarized by treatment and test period (exercise, test meal, in-house period, or overnight), and listed.

The derived CGM parameters will be statistically analyzed for each test period independently using a mixed-effect model. The modified full analysis population will be used for the analysis. The model will include treatment, sequence, and period as fixed effects, and

participant-within-sequence as a random effect. For the in-house and overnight time periods, the categorical variable treatment will have two levels, Lyumjev and Humalog, whereas the exercise and test meal periods will have four levels, Lyumjev with 50% basal reduction, Lyumjev with 100% basal reduction, Humalog with 50% basal reduction, and Humalog with 100% basal reduction. The LS means, difference LS means between Lyumjev and Humalog for corresponding basal rate reduction (test meal and exercise time periods only), difference in LS means between Lyumjev and Humalog (in-house and overnight time periods only), and corresponding 90% CIs, as well as the p-value, will be reported.

If appropriate, the treatment variable for the in-house time period will be changed to use four factors, using the same factors as the test meal and exercise time periods.

9.5.2 Free Fatty Acids and Ketones

Ketone and FFAs levels will be analyzed for the participants during each exercise and MMTT assessment. The mean data will be presented by summary statistics and presented by treatment for those participants who received both treatments (Lyumjev and Humalog) with the same insulin dose (bolus dose for the MMTT or basal reduction) and meal consumption. The data may be presented graphically. A statistical analysis may be conducted upon review of the data. If a statistical analysis is conducted the same or similar model will be used as presented for the glucodynamic endpoints.

9.6 Safety and Tolerability Assessments

9.6.1 Adverse events

Where changes in severity are recorded in the Case Report Form (CRF), each separate severity of the adverse event (AE) will be reported in the listings, only the most severe will be used in the summary tables. A pre-existing condition is defined as a condition that starts before the participant has provided written informed consent and is ongoing at consent. A non-treatment emergent AE is defined as an AE which starts after informed consent but prior to dosing. A TEAE is defined as an AE which occurs postdose or which is present prior to dosing and becomes more severe postdose.

All AEs will be listed. Treatment-emergent AEs will be summarized by treatment, severity and relationship to the study drug. The frequency (the number of AEs, the number of participants experiencing an AE and the percentage of participants experiencing an AE) of treatment-emergent AEs will be summarized by treatment, Medical Dictionary for Regulatory Activities (MedDRA) version 24.1 system organ class and preferred term. The summary and frequency AE tables will be presented for all causalities and those considered related to the study drug by the investigator. Any serious AEs will be listed.

Discontinuations due to AEs will be listed.

9.6.2 Glucose Monitoring and Hypoglycemia

During the study, blood glucose concentrations will be monitored for safety assessments using YSI and CGM (see Section 9.5.9 for further information).

Hypoglycemic events will be appropriately recorded in the CRF. In the case of a hypoglycemic event, the actual blood glucose value, if measured, will be recorded in the CRF, together with any treatments administered. Each category of hypoglycemic events (defined below) will be listed and summarized by treatment. Hypoglycemia is defined as follows:

• Level 1 hypoglycemia:

Glucose CC

- Can alert a person to take action such as treatment with fast-acting carbohydrates. Providers should continue to counsel participants to treat hypoglycemia at this glucose alert value.
- Level 2 hypoglycemia:

Glucose CC

- Also referred to as documented or blood glucose confirmed hypoglycemia with glucose CCI
 This glucose threshold is clinically relevant regardless of the presence or absence of symptoms of hypoglycemia.
- Level 3 hypoglycemia:

Severe hypoglycemia (in adults): A severe event characterized by altered mental and/or physical status requiring assistance for treatment of hypoglycemia. For example, participants had altered mental status, and could not assist in their own care, or were semiconscious or unconscious, or experienced coma with or without seizures, and the assistance of another person was needed to actively administer carbohydrate, glucagon, or other resuscitative actions. Glucose measurements may not be available during such an event, but neurological recovery attributable to the restoration of glucose concentration to normal is considered sufficient evidence that the event was induced by a low glucose concentration.

The determination of a hypoglycemic event as an episode of severe hypoglycemia, as defined above, is made by the investigator based on the medical need of the participant to have required assistance and is not predicated on the report of a participant simply having received assistance.

If a hypoglycemic event meets the criteria of severe hypoglycemia, the investigator must record the event as serious on the AE CRF and report it to Lilly as an SAE.

• Other hypoglycemia:

• **Nocturnal hypoglycemia:** A hypoglycemia event (including severe hypoglycemia) that occurs at night and presumably during sleep

Investigator's review of glucose results clinically indicative of hypoglycemia will be required.

Participants that are administered and consume carbohydrates during the in-house period will be listed.

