### Potential risks associated with CGM use

- Pain, bruising, swelling, redness, and bleeding at the sensor insertion site
- Sensor breakoff where the sensor wire detaches and remains under the skin
- Minor skin irritation, sensitization, or localized inflammatory response can occur if skin contacts bioincompatible materials
- Inaccurate results due to use of meter that is out of calibration, malfunctioning, or rapidly changing glucose levels
- Loss of CGM connectivity (transient and permanent)
- Errors in the data transmitted to the software application
- Electric shock if the device is damaged

The occurrence and severity of these events are not expected to be different from routine use of CGM. More detailed information on the use and about the known and expected risks and potential ADEs may be found in the manufacturer's label and Instructions for Use.

The study includes in-house procedures during which participants will be continuously monitored.

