#### 9.3.2. Glucodynamic Analysis

#### 9.3.2.1. Glucodynamic Parameter Estimation

Participants who receive at least 1 dose of study intervention and have completed at least 1 MMTT procedure will be included in the analysis set for the PD analyses.

Data will be analyzed for the participants during each exercise and MMTT assessment.

During the exercise period, the change from baseline values **CCI** 

for each participant will be

calculated to derive the change in plasma glucose level from start to end of exercise.

The rate of plasma glucose during the exercise, the nadir plasma glucose, decremental AUC, for each exercise assessments will be calculated.

During the MMTT, the change from baseline values **CC** 

for each participant will

be calculated. The area under the baseline subtracted plasma glucose concentration versus time curve (incremental) (iAUC) will be calculated during the MMTT for each in-house period.

- The AUC from time zero to 30 minutes postmeal (iAUC0-30min)
- The AUC from time zero to 1-hour postmeal (iAUC0-1hour)
- The AUC from time zero to 2 hours postmeal (iAUC0-2hours)
- The AUC from time zero to 3 hours postmeal (iAUC0-3hours)
- The AUC from time zero to 4 hours postmeal (iAUC0-4hours)

In addition, the change from baseline maximum plasma glucose observed during the 4 hours postmeal ( $\Delta$ PGmax) and change from baseline 1-hour plasma glucose ( $\Delta$ PG1h and 2-hour plasma glucose after the start of the meal ( $\Delta$ PG2h) will be calculated. Other partial iAUCs may be calculated, as deemed appropriate.

The mean data will be presented by summary statistics and presented by treatment for those participants who received both treatments (Lyumjev and Humalog) with the same insulin dose (bolus dose for the MMTT or basal reduction) and meal consumption.

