## 9.3.2.2. Glucodynamic Statistical Inference

Statistical analyses comparing PD parameters (described in Section 9.3.2.1) of Lyumjev versus Humalog during exercise with a basal reduction of either 50% or 100% and after the MMTT will be conducted on the modified full analysis set. The exercise and MMTT will be analyzed separately.

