4.2 Secondary Objectives and Endpoints

The secondary objectives of the study are:

- To compare the glucodynamic response with Lyumjev versus Humalog during a dinner mixed-meal tolerance test (MMTT) following moderate-intensity aerobic exercise using either 50% or 100% reduction of basal infusion rates, set 60 minutes or 15 minutes before the onset of exercise, respectively
- To compare the PK of insulin lispro between Lyumjev versus Humalog during an MMTT
- To compare the PK of insulin lispro between Lyumjev versus Humalog during 60 minutes of moderate-intensity aerobic exercise using either 50% or 100% reduction of basal infusion rates with Lyumjev or Humalog, set 60 minutes or 15 minutes before the onset of exercise, respectively.

The secondary endpoints of the study are:

- Postprandial PG excursion during the test meal (e.g., area under the plasma concentration versus time curve [AUC] from time 0 to 4 hours [AUC{0-4h}])
- Insulin lispro PK during the MMTT after exercise
- Insulin lispro PK during the exercise.

4.3 **Exploratory Objectives and Endpoints**

The exploratory objectives of the study are:

- To investigate tolerability and safety of Lyumjev and/or Humalog
- To perform an exploratory comparison of glucose variability, time in range, hypoglycemia, and hyperglycemia using continuous glucose monitoring (CGM) profiles obtained from participants receiving Lyumjev and Humalog.

The exploratory endpoints of the study are:

- Incidence of treatment-emergent adverse events (TEAEs), serious adverse events (SAEs), symptomatic hypoglycemia
- Blood ketone levels
- Overall variability (coefficient of variation [CV] and standard deviation [SD])
- Time in range (70 to 180 mg/dL) during exercise, MMTT assessment, overnight period, and for the entire in-house period
- Time in hypoglycemia (<70 and <54 mg/dL) and hyperglycemia (>180 and 140 mg/dL)
- Mean glucose levels.

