Following completion of glucose sampling, the CCI will be removed and the participant's own insulin pump will be re-introduced using a new infusion set, if necessary, for pump compatibility.

Figure 1: Study activities during Assessment day (Visit 2)

In-house Visits (Visits 3, 4, 5, and 6)

After Visit 2, all eligible participants will undergo 4 in-house study periods (Visits 3 to 6). Each in-house period will comprise a 2-day stay at the CRU. The in-house period will be separated by a washout period of **CCI** (e.g., between Visit 3, Day 1 and Visit 4, Day 1). Each participant will be randomly assigned to a treatment sequence consisting of 2 treatments (blinded), i.e., Lyumjev and Humalog, and 2 different basal insulin reduction rates to be administered at the 4 separate in-house visits in 4 by 4 crossover Williams design. Randomization will take place on Day -1 of Visit 3.

Upon arrival at the site, participants will be placed on a standardized insulin pump CCI				
with a new in	fusion set	and a CGM		
system CC	on the evening before the exercise session			

After disconnecting the participant's own insulin pump, the study pump reservoir will be filled with either Lyumjev or Humalog by a qualified CRU staff, and a standard infusion set and catheter will be inserted into the abdominal area, as per the manufacturer's instructions, after the region is inspected for lipodystrophy. The catheter should stay at the same catheter insertion site location for the duration of each period. However, a catheter can be changed to a new location on the abdomen if an occlusion is suspected up to the breakfast meal on Day 1. The participant's usual basal rate settings will be programmed in the pump and the basal rate infusion will be started.

The participants will wear the CRU-provided pump and CGM device during all in-house days. The CGM device will be calibrated on the morning of the exercise day in fasted state, if needed, using the PG values obtained with a glucose analyzer by CRU staff.

A standardized dinner will be provided at approximately CCL On Day 1, a standardized breakfast (CCL) and lunch (CCL) will be provided prior to the scheduled exercise assessment (CCL The insulin dose for these standardized meals (dinner, breakfast, and lunch) before exercise will be individualized per participant to cover the carbohydrate content (including any correction bolus) and will be administered immediately prior (0 to 2 minutes) to the meal using a CCL

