6. TREATMENTS

The following is a list of the study treatment abbreviations that will be used in the TFLs.

Study Treatment Name	Abbreviation	Treatment order in TFL
Lyumjev with 50% basal rate reduction	Treatment A	1
Lyumjev with 100% basal rate reduction	Treatment B	2

Humalog with 50% basal rate reduction	Treatment C	3
	Treatment D	4
Humalog with 100% basal rate reduction		4

The following is a list of the study treatment sequences that will be used in the demographics and vital signs TFLs.

Study Treatment Sequence	Abbreviation	Treatment order in TFL
Treatment A/ Treatment D/ Treatment B/ Treatment C	A/D/B/C	1
Treatment B/ Treatment A/ Treatment C/ Treatment D	B/A/C/D	2
Treatment C/ Treatment B/ Treatment D/ Treatment A	C/B/D/A	3
Treatment D/ Treatment C/ Treatment A/ Treatment B	D/C/A/B	4

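### Hypoglycemic events have no exercise window, the symptomatic endpoint has no matching category, and nadir glucose is in no SAP model

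*SAP*

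**What the plan says.** **Events.** SAP 9.6.2 covers Levels 1, 2 and 3 and nocturnal hypoglycemia: "Each category of hypoglycemic events (defined below) will be listed and summarized by treatment". No period of the stay is named. The section refers to an SAP Section 9.5.9 for more on glucose monitoring, but SAP 9.5 ends at 9.5.2, so no window can be found there. SAP 9.6.9 plans no inference on safety data. Carbohydrate given during the stay is only listed.

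**Treatment labels.** SAP 6 introduces A to D with "The following is a list of the study treatment abbreviations that will be used in the TFLs". A and B are Lyumjev with the 50% and 100% basal reduction; C and D are Humalog with the same two. The participant goes onto the study pump "on the evening before the exercise session" (SAP 5).

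**CGM.** SAP 9.5.1 treats the stay differently: "For the in-house and overnight time periods, the categorical variable treatment will have two levels, Lyumjev and Humalog". Exercise and test meal have four levels. Time below 70 and 54 mg/dL is modelled for each test period with 90% CIs and p-values.

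**Symptomatic events.** SAP 4.3 lists as an exploratory endpoint: "Incidence of treatment-emergent adverse events (TEAEs), serious adverse events (SAEs), symptomatic hypoglycemia".

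**Nadir.** Protocol 9.3.2.1 says "the nadir plasma glucose, decremental AUC, for each exercise assessments will be calculated". Protocol 9.3.2.2 then plans "Statistical analyses comparing PD parameters (described in Section 9.3.2.1) of Lyumjev versus Humalog during exercise". SAP 9.4.1 derives nadir and summarises the glucodynamic data by treatment. SAP 11 declares no changes from the protocol's analyses.

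**The concern.** The trial's title is about protection from exercise-induced hypoglycemia. A reader will look for how often glucose fell too low during and shortly after exercise on each product, at each basal reduction. The SAP does not specify a table that answers this from plasma glucose. Its event table has no window, so events from the evening, night and morning before exercise can be counted together with exercise events and split by a reduction that had not started. Nadir, the derived plasma glucose measure closest to hypoglycemia, gets no planned comparison. At stake are a diluted view of any product difference in exercise hypoglycemia and a chance imbalance in earlier events that could be read as an effect of the basal reduction.

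**Working it through.** **The plan's own figure.** The documents give no figure for hypoglycemia. The only sizing statement (SAP 7) concerns the mean change in plasma glucose: 28 completers, 14 mg/dL, SD 27.9, two-sided alpha 0.10, about 80% power. Taking 27.9 as the SD of the within-participant difference, n = (27.9 × (1.645 + 0.842) / 14)² = 24.6 by the normal formula and 26 by the paired t-test; 28 completers give 82.7%. It reproduces closely, and this point does not change it.

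**Clock times.**

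- Exercise starts at about 3 PM (SAP 5) and lasts 1 hour, to 4 PM.
- The basal reduction starts 60 minutes before (2:00 PM, 50%) or 15 minutes before (2:45 PM, 100%).
- The MMTT follows exercise by about 1 hour (Protocol 4.1.3), so it starts at 5 PM. Sampling runs 4 hours, to 9 PM. The 9 PM cannula removal in the protocol's summary of changes agrees.
- Pump start is in the evening of Day -1. The time is redacted; 4 PM to 8 PM is assumed.

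Total hours = pump start to 9 PM on Day 1 = 29 h (4 PM start) down to 25 h (8 PM start). Share = segment hours / total hours.

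| Segment | 50% reduction | 100% reduction |
|---|---|---|
| Pump start to reduction | 18 to 22 h: 18/25 = 72.0% to 22/29 = 75.9% | 18.75 to 22.75 h: 18.75/25 = 75.0% to 22.75/29 = 78.4% |
| Reduction to MMTT start | 3 h: 10.3% to 12.0% | 2.25 h: 7.8% to 9.0% |
| of which the exercise hour | 1 h: 3.4% to 4.0% | 1 h: 3.4% to 4.0% |
| MMTT | 4 h: 13.8% to 16.0% | 4 h: 13.8% to 16.0% |

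About three quarters of the hours come before the feature that separates A from B and C from D. The only in-house night is the one before exercise, so any A versus B or C versus D difference in in-house nocturnal events cannot come from that visit's basal reduction.

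**What mixing does.** Suppose a share f of the reference product's events falls between basal reduction and MMTT, and the products do not differ elsewhere. A relative difference d in that window then appears as f × d in the unwindowed total. The expected difference in counts is unchanged, but the other events add noise. The documents give no event rates, so f could lie anywhere from 0 to 1. It would equal the 8% to 12% share of hours only if the event rate were constant over the stay.

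**Symptomatic events.** In the text left visible, Level 1 states no symptom criterion, Level 2 applies with or without symptoms, and Level 3 is symptomatic by definition. None of the listed categories is symptomatic hypoglycemia as such.

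**Nadir.** SAP 9.4.2 names these for a model: change in plasma glucose, iAUCs, ΔPGmax, ΔPG1h, ΔPG2h, AUCs during exercise, rate of change, and exploratory time parameters. Nadir is none of these.

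**The case against.** The strongest reply is that the SAP does address the exercise question. The primary endpoint is the change in plasma glucose over exercise; exercise AUC and rate of change are modelled; and CGM time below 70 and 54 mg/dL during exercise is compared between products at each basal reduction. This stands. A reader might infer that protection from exercise hypoglycemia is not measured at all, and the documents do not support that.

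Several narrower replies also stand:

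- A reader might infer that the event table is set to cover the whole stay. The SAP says neither that nor the opposite. The window is undefined, and the table shells are a separate document not available here.
- A reader might infer bias between products. The product comparisons in SAP 9.4.2 and 9.5.1 are within the same reduction (A with C, B with D), and the order is randomised. Earlier events therefore dilute and add noise rather than favour one product systematically. The products also differ from pump start, so earlier events are genuine product safety data.
- Share of hours is not share of events. Exercise may well concentrate the risk.
- A reader might infer that symptomatic events will never be reported. Protocol 9.3.5 promises the incidence of symptoms by treatment, adverse events are tabulated by preferred term, and the case report form is not available. What can be said is that SAP 9.6.2 defines no such output.
- Nadir is summarised by treatment, and Protocol 9.3.2.2.2 does not name it in a model either. The commitment to compare it rests on the general sentence in Protocol 9.3.2.2.
- The protocol's CGM caution, "Inaccurate results due to use of meter that is out of calibration, malfunctioning, or rapidly changing glucose levels", is one item in a general list of device risks, and calibration to plasma glucose is allowed if needed. It adds only modest weight.

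These replies do not fill the gap. The mean glucose change does not show how many sessions were stopped, since Protocol 4.1.3 ends exercise and gives carbohydrate when hypoglycemia occurs, and the SAP specifies no count of such sessions. YSI glucose is sampled during exercise, yet the SAP specifies no count of low values in that window.

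**Conclusion.** The point holds as a gap in the descriptive and exploratory outputs; the primary analysis is untouched. Three things are established from the text: events are summarised by treatment with no window, the symptomatic endpoint has no matching category in SAP 9.6.2, and nadir has no model in SAP 9.4.2 although Protocol 9.3.2.2 says it is compared and SAP 11 reports no changes. Formal comparison of hypoglycemia in the exercise window rests on exploratory CGM time below range alone.

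Under the assumed pump start of 4 PM to 8 PM, 72% to 78% of the in-house hours precede the basal reduction, and the conclusion is the same across that range. This measures how much unrelated time an unwindowed table can take in. How far an exercise difference would be diluted cannot be calculated without event rates. A change is worthwhile because the missing outputs bear directly on the question in the title and use data already planned.

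**What to change.** 1. In SAP 9.6.2, summarise events in three windows: pump start to basal reduction, by product only (as SAP 9.5.1 does for overnight CGM); basal reduction to MMTT start, by A to D; and MMTT, by A to D. For the middle window, report for each treatment the number and proportion of sessions with YSI glucose below 70 and below 54 mg/dL (the SAP 9.5.1 cut-offs), and of sessions stopped or given carbohydrate for hypoglycemia. Add the descriptive Lyumjev-Humalog difference within each basal reduction. Note beside the table that treating hypoglycemia truncates the counts below 54 mg/dL.
2. Add nadir plasma glucose, untransformed, to the parameters analysed with the SAP 9.4.2 mixed model. Read it with the count of stopped sessions, because stopping exercise can also limit how low nadir falls.
3. Tabulate symptomatic events by window, using the recorded symptom status. Sites already have to judge symptoms when deciding on treatment of Level 1 events during the MMTT (Protocol 4.1.3 and 8.2.7.2). Confirm that the case report form holds this status; if it does not, a yes/no field is needed.
4. Correct the reference to Section 9.5.9.

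The cost is SAP and table-shell wording and one more model, with no new samples and no change in sample size or clinical procedures. The drawback is small counts per window, so the event comparison is descriptive and should be labelled so.
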